1. PROTOCOL SYNOPSIS FOR STUDY 201023

Rationale

Seasonal influenza affects 5-10% of the world's population annually, causing 3-5 million severe infections and 250,000 – 500,000 deaths. While early therapy with antivirals decreases severity and duration of symptoms of influenza, there are no drugs that have demonstrated clinical efficacy in randomized clinical trials in this population. Current treatment guidelines for hospitalized influenza recommend neuraminidase inhibitors as standard of care therapy. Following infection by a respiratory virus, neutrophils are the most abundant cells that migrate to the lungs. Influenza studies in animals have demonstrated that therapeutic treatment with the combination of a C-X-C chemokine receptor 2 (CXCR2) antagonist and a neuraminidase inhibitor reduced lung neutrophils and showed trends for improvements in clinical scores, lung function and pathology with no evidence of worsening outcomes, including viral load.

This study is designed to investigate an anti-inflammatory agent, danirixin (DNX; GSK1325756) co-administered with an antiviral treatment oseltamivir (OSV) for treatment of patients hospitalized for influenza infection and will be the first study to evaluate the efficacy and safety of intravenous DNX in this population.

Objective(s)/Endpoint(s)

Objectives	Endpoints
Primary	

 To assess the efficacy of treatment with IV DNX twice daily given with oral oseltamivir compared to oral oseltamivir twice daily on time to clinical response (TTCR) 	
 Time to Clinical Response (composite) 
 Hospital discharge OR Normalization of: 
 -- Temperature; and --Oxygen saturation; and --Respiratory status/Heart Rate/Systolic BP (SBP) (normalization of 2 out of these 3 parameters)
Secondary	

 To assess the efficacy of treatment with IV DNX twice daily given with oral oseltamivir compared to oral oseltamivir twice daily on time to respiratory response (TTRR) 	
 Time to Respiratory Response defined as meeting at least one criterion below 
 Return to pre-morbid oxygen requirement (subjects with chronic oxygen use), OR Return to no requirement of supplemental oxygen, OR

Objectives	Endpoints
	
 • Respiratory rate ≤ 24/min (without supplemental oxygen)

 • To evaluate clinical measures of influenza illness following treatment with IV DNX twice daily given with oral oseltamivir compared to oral oseltamivir twice daily 	
 • Time to absence of fever • Time to improved oxygen saturation • Time to improved heart rate • Time to improved SBP • Proportion of subjects with clinical response over time • Proportion of subjects with improved respiratory status over time • Time to improvement of ventilation status: modality, frequencies and durations of invasive and non-invasive ventilator support, duration of oxygen supplementation. • Length of stay in the Intensive care unit (ICU) • Frequency of ICU admission and readmission • Length of stay in the hospital • Rates of development of septic shock • Frequency of antibiotic use • Proportion of subjects with improvement in Ordinal scale of clinical efficacy over time : 
 • Death • Mechanical vent • In the ICU • Non-ICU hospitalization • Hospital discharge

 • To characterize the safety and tolerability of IV DNX twice daily given with oral oseltamivir compared to oral oseltamivir twice daily 	
 • Frequency of adverse events (AEs) and serious adverse events (SAEs) • Frequency of adverse events of special interest (AESIs) • Change from baseline in clinical laboratory evaluations, and electro

Objectives	Endpoints
	cardiogram (ECG) parameters

 To characterize the pharmacokinetics of IV DNX in subjects hospitalized for influenza 	
 Standard pharmacokinetic parameters for IV DNX (i.e. area under the curve [AUC], maximum observed concentration [Cmax], average concentration [Cavg]).

Overall Design

This study is a Phase 2, randomized, double-blind (for IV DNX), placebo-controlled (for IV DNX) 3-arm study in adults to determine the efficacy and safety of IV DNX when co-administered (in all groups) with standard of care antiviral treatment (open-label oral 75 mg OSV) for patients hospitalized with influenza.

An Independent Data Monitoring Committee (IDMC) will perform monitoring and reviews of available safety and efficacy data. In the first influenza season, the IDMC will review unblinded safety data across all study cohorts, after every approximately 10-20 subjects have completed the post-treatment (PT) Day 3 visit. Frequency of IDMC reviews in subsequent seasons will be determined based on safety results of the interim analysis.

Treatment Arms and Duration

Subjects will be randomized in a 2:2:1 ratio to receive:

- 15 mg FBE IV DNX +75 mg OSV;
- 50 mg FBE IV DNX+75 mg OSV; or
- IV DNX placebo+75 mg OSV

Treatment duration will be 5 days. The investigator may elect to continue open-label oseltamivir treatment. Follow up will continue until Day 45 for all subjects.

Type and Number of Subjects

The study will recruit adult patients with influenza infection requiring hospitalization. Influenza patients with conditions of respiratory failure requiring mechanical ventilation, chronic kidney disease, acute renal failure, sepsis, or hemodynamic instability are considered a more severe population.

A maximum of 300 subjects are planned to be enrolled in the study, depending on study dose changes implemented after each of two planned interim analyses. Interim analyses are planned after each influenza season if there are more than 75 subjects enrolled. Completion of enrolment in this study is expected to take multiple influenza seasons.

Analysis

The sample size of 300 was selected based on simulations to achieve at least 80% overall power under assumption of HR =1.5 for 50 mg of DNX FBE and HR =1.2 for 15 mg of DNX FBE and keep type I error less than 10% under no-effect assumption.

An adaptive design is employed that allows for dropping a dose at interim analyses. These interim analyses also allow for early stopping for futility or efficacy. Probability of success for efficacy will be calculated, defined as a statistically significant treatment effect ($p\text{-value} < 0.025$ for hazard ratio of TTCR > 1) in a future two-arm comparative superiority study with 300 subjects per arm, given observed data.

Exposure to study medication, measured by the number of days on study drug, will be summarized by treatment arm. The proportion of subjects reporting adverse events (AEs) will be tabulated for each treatment arm.

2. INTRODUCTION

GSK1325756 (danirixin; DNX) is a novel, potent, selective, and reversible antagonist of the C-X-C chemokine receptor (CXCR) 2 and has been shown to decrease neutrophil transmigration and activation to areas of inflammation. An intravenous (IV) solution for infusion is being developed as an anti-inflammatory agent for hospitalized influenza (IFV) patients. Clinical development of an oral formulation for the treatment of chronic obstructive pulmonary disease (COPD) has also commenced.

Severe viral respiratory tract infections can cause direct injury through cytopathicity as well as tissue damage through an excessive immune response [Garcia, 2010; Perrone, 2008]. Selective CXCR2 antagonists potentially maintain a balance between inhibiting excessive immune response while preserving antimicrobial function by only partially reducing neutrophils, selectively inhibiting CXCR2 over CXCR1 (CXCR1 is involved in neutrophil degranulation), and maintaining acquired humoral immunity and cell-mediated immunity [Jones, 1996; Hartl, 2007; Seiberling, 2013; GSK Document Number YM2010/00163/07].

2.1. Study Rationale

This study is designed to investigate an anti-inflammatory agent (DNX) co-administered with an antiviral treatment (OSV) for treatment of patients hospitalized for influenza infection.

Seasonal influenza affects 5-10% of the world's population annually, causing 3-5 million severe infections and 250,000 – 500,000 deaths [Hayward, 2014]. While early therapy with antivirals decreases severity and duration of symptoms of influenza, there are no drugs that have demonstrated clinical efficacy in randomized clinical trials in this population. Current treatment guidelines for hospitalized influenza recommend neuraminidase inhibitors as standard of care therapy.

Following infection by a respiratory virus, neutrophils are the most abundant cells that migrate to the lungs, and excessive migration has been demonstrated to cause lung damage through release of tissue-destructive enzymes and reactive oxygen species and formation of neutrophil extracellular traps [Narasaraju, 2011]. Respiratory neutrophil levels and/or their associated chemokines involved in recruitment are correlated with clinical symptom severity of influenza infection in humans [Taubenberger, 2008; Short, 2014; Hayden, 1998].

Influenza studies in animals have demonstrated that therapeutic treatment with the combination of a CXCR2 antagonist and a neuraminidase inhibitor reduced lung neutrophils and showed trends for improvements in clinical scores, lung function and pathology with no evidence of worsening outcomes, including viral load [GSK Document Number YM2010/00163/07]. In addition, nonclinical and clinical studies support the hypothesis that selective antagonism of CXCR2 has an acceptable safety profile [GSK Document Number YM2010/00163/07].

This will be the first study to evaluate efficacy and safety of intravenous DNX (GSK1325756) given with a standard-of-care antiviral, oral oseltamivir (OSV), for

treatment of patients hospitalized with influenza infection. An IV formulation of DNX, danirixin hydrobromide (DNX HBr) has been developed and will be used for treatment in this study, since parenteral administration would be a preferred mode of delivery of medication in this hospitalized population, especially in critically ill patients. In this document, the IV DNX HBr dose will be presented as the free base equivalent (FBE).

2.2. Brief Background

Danirixin free base (DNX-FB) has undergone a comprehensive non-clinical assessment, including 39-week dog and 26-week rat toxicology studies, during which no signals were observed that might preclude further assessment in clinical trials. DNX-HBr has undergone a 4-week rat bridging toxicity study, a 14 day mouse pre-oncogenicity study and a full non-clinical assessment of reproductive toxicology comprising rat and rabbit embryofetal development studies in addition to male and female rat fertility studies.

A summary of the nonclinical information for DNX-FB and DNX-HBr, including a list of nonclinical Pharmacodynamic, Pharmacokinetic & Product Metabolism and Toxicology studies completed to date is provided in Section 4 of the Investigator's Brochure (IB) [GSK Document Number [YM2010/00163/07](#)].

Across the COPD and IFV programs, the number of subjects exposed to DNX is approximately 270. Six phase 1 clinical studies in healthy volunteers (HV) have been completed using oral and IV DNX treatment and over 180 HV subjects have been treated with DNX (10-400 mg DNX). The HV studies initially utilized the FB oral (up to 400 mg) and IV formulations of DNX (up to 50 mg twice daily (BID) for 5 days or 100 mg single dose). Most recently, Study 201037 in elderly HV has used the oral HBr formulation of DNX (50 mg single dose). Study 201682/DAISI was a phase II placebo-controlled study in uncomplicated outpatient influenza subjects (N=45). Subjects were treated with 75 mg oral DNX or placebo (PBO) BID and 75 mg oral OSV or PBO BID for 5 days. Safety of DNX treatment in the IFV population is being studied in a staged manner. DAISI was conducted in an outpatient IFV population prior to this study which investigates DNX treatment in less severe hospitalized subjects, followed by critically ill hospitalized subjects this study (Study 201023; DAHLIA). In DAHLIA, the HBr formulation of DNX will be provided as an IV infusion. Further information is located in the Investigator's Brochure [GSK Document Number [YM2010/00163/07](#)].

3. OBJECTIVES AND ENDPOINTS

Objectives	Endpoints
Primary	

 To assess the efficacy of treatment with IV DNX twice daily given with oral oseltamivir compared to oral oseltamivir twice daily on time to clinical response (TTCR) 	
 Time to Clinical Response (composite) 
 Hospital discharge OR 
 Normalization of: 
 -- Temperature; and --Oxygen saturation; and --Respiratory status/Heart Rate/SBP (normalization of 2 out of these 3 parameters)
Secondary	

 To assess the efficacy of treatment with IV DNX twice daily given with oral oseltamivir compared to oral oseltamivir twice daily on time to respiratory response (TTRR) 	
 Time to Respiratory Response defined as meeting at least one criterion below 
 Return to pre-morbid oxygen requirement (subjects with chronic oxygen use), OR Return to no requirement of supplemental oxygen, OR Respiratory rate ≤ 24/min (without supplemental oxygen)

 To evaluate clinical measures of influenza illness following treatment with IV DNX twice daily given with oral oseltamivir compared to oral oseltamivir twice daily 	
 Time to absence of fever Time to improved oxygen saturation Time to improved heart rate Time to improved SBP Proportion of subjects with clinical response over time Proportion of subjects with improved respiratory status over time Time to improvement of ventilation status: modality, frequencies and durations of invasive and non-invasive ventilator support, duration of oxygen supplementation. Length of stay in the ICU Frequency of ICU admission and

Objectives	Endpoints
	readmission 
 • Length of stay in the hospital • Rates of development of septic shock • Frequency of antibiotic use • Proportion of subjects with improvement in Ordinal scale of clinical efficacy over time : 
 • Death • Mechanical vent • In the ICU • Non-ICU hospitalization • Hospital discharge

 • To characterize the safety and tolerability of IV DNX twice daily given with oral oseltamivir compared to oral oseltamivir twice daily 	
 • Frequency of adverse events (AEs) and serious adverse events (SAEs) • Frequency of adverse events of special interest (AESIs) • Change from baseline in clinical laboratory evaluations, and ECG parameters

 • To characterize the pharmacokinetics of IV DNX in subjects hospitalized for influenza 	
 • Standard pharmacokinetic parameters for IV DNX (i.e. AUC, Cmax, Cavg).
Exploratory	

 • To assess changes in influenza viral load from nasopharyngeal swabs following treatment with IV DNX twice daily given with oral oseltamivir compared to oral OSV twice daily; perform resistance analysis and a multiplex PCR assay with respiratory virus panel to assess co-infection. 	
 • Change in quantitative influenza viral load over time and change from baseline measured from nasopharyngeal swab samples and lower respiratory tract samples, as determined by qRT-PCR and quantitative virus culture (qVC) • Percentage of subjects with no detectable influenza viral RNA by qRT-PCR and qVC. • Percentage of subjects with co-infected viruses by multiplex RT PCR. • Percentage by type of co-infected viruses by multiplex RT PCR. • Change in quantitative viral load of other virus co-infections over time and

Objectives	Endpoints
	change from baseline measured from nasopharyngeal swab samples and lower respiratory tract samples, as determined by qRT-PCR. 
 • Frequency of emergent resistance to OSV

 • To explore the effects of IV DNX twice daily given with oral oseltamivir compared to oral OSV twice daily with IV DNX placebo on biomarkers of inflammation and immune response from nasal samples or fluid, endotracheal samples, whole blood, bronchoalveolar lavage, and/or serum. 	
 • Quantitative and qualitative changes in exploratory biomarkers (may include but are not limited to: IL-8, procalcitonin, respiratory neutrophil cell counts, neutrophil elastase, and myeloperoxidase).

 • To characterize the PK response relationship of IV DNX. 	
 • PK exposure for DNX and pharmacodynamic parameters.

 • To determine health outcome impact of IV DNX twice daily given with oral OSV compared to oral OSV twice daily 	
 • FLU PRO questionnaire • Activities of daily living (Katz ADL Score) • Activity level • Hospital readmission rates

4. STUDY DESIGN

4.1. Overall Design

This study is a Phase 2, randomized, double-blind (for IV DNX), placebo-controlled (for IV DNX) 3-arm study in adults to determine the efficacy and safety of IV DNX when co-administered (in all groups) with standard of care antiviral treatment (open-label oral 75 mg OSV) for patients hospitalized with influenza.

Subjects will be assessed for influenza with a rapid diagnostic test provided by GlaxoSmithKline (GSK) (such as next generation rapid antigen test, commercial reverse transcriptase-polymerase chain reaction [RT-PCR], molecular assay), or local influenza test. A confirmatory RT-PCR test will be done by the central laboratory. Following confirmation of influenza with a rapid-diagnostic test, and meeting all other eligibility criteria, subjects will enter the study. Subjects will receive one of two doses of DNX given as an IV infusion, twice daily. Enrollment of subjects will be in a 2:2:1 ratio of 15 mg FBE IV DNX, 50 mg FBE IV DNX, or matching placebo. All subjects will also receive open-label oral OSV, twice daily (given as standard of care). Study treatment duration will be for up to 5 days. The investigator may elect to continue treatment with OSV after 5 days of study treatment.

The study will begin with enhanced safety monitoring in sentinel cohorts, leading to step-wise enrollment of subjects. Subjects will be enrolled based on increasing levels of renal impairment (Section 4.1.1), and less severe hospitalized subjects will be enrolled prior to enrollment of a critically ill subjects (Section 4.1.2 and Section 4.3), as this is the first study conducted in the hospitalized population with severe influenza.

Approximately 100 subjects are targeted to be enrolled in the study in the first influenza season and up to 100 subjects are planned to be enrolled in each of two additional influenza seasons for a total of approximately 300 subjects in the study.

Pharmacokinetic analysis will be done in batches during the study to provide confirmation of exposure to DNX. Similarly, to obtain evidence of target engagement, nasal and/or endotracheal samples may be evaluated in batches to determine respiratory biomarker (neutrophil) patterns following treatment with DNX.

Interim analyses of efficacy and safety data will be conducted to confirm dose regimens for subjects in the remainder of the influenza seasons. The first interim analyses will occur after the first flu season if there are more than 75 subjects enrolled. Additional interim analyses may be performed after approximately 50-66% of subjects have been enrolled.

Four potential outcomes of the interim analysis include the following: (1) stop the study for safety reasons, (2) stop the study for futility or efficacy, (3) continue with one DNX dose arm, or (4) continue with the two original DNX arms. The Bayesian decision criteria with regards to TTCR together with other efficacy, pharmacokinetic (PK) and safety data will be provided to support decisions on dose selection and study stopping after each interim analysis.

An Independent Data Monitoring Committee (IDMC) will perform monitoring and reviews of available safety and efficacy data. In the first influenza season, the IDMC will review unblinded safety data across all study cohorts, after every approximately 10-20 subjects have completed the post-treatment (PT) Day 3 visit. Study halting and dose arm halting criteria have been designed to guide IDMC review and decisions (summarized in Section 10.8.1 and detailed in the IDMC charter). Frequency of IDMC reviews in subsequent seasons will be determined based on safety results of the interim analysis.

The final analysis will occur when both accrual and follow-up are complete for all subjects. Formal statistical decision rules of interim and final analysis for TTCR are defined in Section 9.

4.1.1. Sentinel Cohorts with Enhanced Safety Monitoring

Sentinel cohorts with enhanced safety monitoring will be enrolled as part of a step-wise enrollment of subjects with different levels of renal impairment and disease severity (less severe and critically ill, Section 4.3). Subjects in the sentinel cohorts will have more stringent eligibility criteria (baseline creatinine clearance criteria and exclusion of subjects with diabetes mellitus and chronic kidney disease). The IV DNX formulation developed for this study contains 750 mg β -Cyclodextrin Sulfobutylether (SBE- β -CD, Captisol) per 50 mg of GSK1325756 (free base equivalent [FBE]), to achieve the desired

[figure not shown]
5mg/mL concentration (FBE) and ensure DNX remains in solution when added to the IV saline bag. Captisol is renally cleared with the potential for accumulation in subjects with severe renal impairment. As such, this study includes enhanced monitoring to evaluate for renal function. Subjects in the sentinel cohorts will undergo serum creatinine, eGFR and urine output assessments twice a day for the treatment period. Additional enhanced monitoring will be based on disease severity, peripheral neutropenia and bacterial infections.

Approximately 30 subjects who are less severely ill and have baseline creatinine clearance within normal reference ranges (creatinine clearance ≥ 80 mL/min) will be enrolled in sentinel cohort 1 (Figure 1). The IDMC will first review available safety data after completion of the PT Day 3 visit, from approximately 10 subjects who are less severely ill and have normal renal function enrolled in sentinel cohort 1. Enrollment of subjects with normal renal function will continue during this review.

Following a review of all available data from the approximately 30 subjects in sentinel cohort 1, and an acceptable outcome from the IDMC, approximately 10 subjects with mild renal impairment, defined as baseline creatinine clearance of 50-79 mL/min will be enrolled in sentinel cohort 2, while continuing to enroll subjects with normal renal function in the study. At this stage, both less severely ill and the more critically ill subjects may be enrolled.

The IDMC will review the available safety data after completion of PT Day 3 from subjects in sentinel cohort 2 with mild renal impairment. Additional subjects with mild renal impairment will not be enrolled until the safety review is conducted by the IDMC, and the determination of an acceptable outcome.

Following an acceptable outcome from the IDMC review of the subjects with mild renal impairment, further enrollment of subjects with mild renal impairment will resume and approximately 10 subjects with moderate renal impairment (defined as baseline creatinine clearance of 30-49 mL/min) will be enrolled in sentinel cohort 3. The IDMC will review the available safety data after PT Day 3 from subjects in sentinel cohort 3 with moderate renal impairment. Following an acceptable outcome from the IDMC review, additional subjects with moderate renal impairment may be enrolled in the study.

Figure 1 Enrollment and Evaluation in Sentinel Cohorts

NOTE: CrCL = creatinine clearance

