Renal Risk	
The IV formulation of DNX contains Captisol that is renally cleared and has a potential for accumulation in renally impaired patients.
 
Healthy volunteers have been dosed in a phase 1 study with an IV DNX formulation containing higher concentrations of Captisol with no safety concerns.
	
The study has intensive renal monitoring and stepwise inclusion of subjects with normal renal function followed by subjects with mild and then moderate renal impairment after review by an IDMC. The IDMC will include an ad hoc nephrologist member if there are 10 subjects across all treatment arms withdrawn due to the renal stopping criteria or if renal expertise is needed.
 
Subjects with CrCl <30 mL/min will be excluded from the study.
 
At the current doses, the Captisol concentrations in subjects with CrCl >30 mL/min are predicted to be below that obtained clinically with marketed Captisol containing IV voriconazole.

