- 6. Onset of influenza symptoms within 6 days prior to study enrolment. Symptoms may include cough, dyspnea, sore throat, feverishness, myalgias, headache, nasal symptoms (rhinorrhea, congestion), fatigue, diarrhea, nausea and vomiting.
- 7. A positive result from a rapid influenza test (provided by GSK) or other available, local laboratory diagnostic test;
- 8. Baseline renal criteria as follows:

Sentinel Cohorts:

- Normal renal function: Baseline creatinine clearance within normal reference ranges (≥ 80 mL/min) for the first approximately 30 subjects enrolled;
- Mild renal impairment: Baseline creatinine clearance of 50-79 mL/min for the next approximately 10 subjects enrolled into the sentinel cohort;
- Moderate renal impairment: Baseline creatinine clearance of 30-49 mL/min for the next approximately 10 subjects enrolled into the sentinel cohort.

Post-sentinel cohorts:

- Normal renal function, mild or moderate renal impairment: creatinine clearance > 30 mL/min.

9. Baseline Liver Function Tests as follows:

Liver parameter	ALT \leq 5xULN	ALT $>$ 5 and \leq 8xULN	ALT $>$ 8xULN
Bilirubin \leq 2x ULN	Include	Include only if bilirubin $<$ 1.5xULN	Exclude
Bilirubin $>$ 2x ULN	Exclude	Exclude	Exclude

SEX

10. Male or Female subjects could be eligible if :

Males:

Male subjects with female partners of child bearing potential must comply with the

following contraception requirements from the time of first dose of study medication until at least 36 hours (five half-lives) after the last dose of study medication.

- a. Vasectomy with documentation of azoospermia.
- b. Male condom plus partner use of one of the contraceptive options below:
 - Contraceptive subdermal implant
 - Intrauterine device or intrauterine system
 - Oral Contraceptive, either combined or progestogen alone [[Hatcher, 2007a](#)]
Injectable progestogen [[Hatcher, 2007a](#)]
 - Contraceptive vaginal ring [[Hatcher, 2007a](#)]
 - Percutaneous contraceptive patches [[Hatcher, 2007a](#)]

This is an all-inclusive list of those methods that meet the following GSK definition of highly effective: having a failure rate of less than 1% per year when used consistently and correctly and, when applicable, in accordance with the product label. For non-product methods (e.g., male sterility), the investigator determines what is consistent and correct use. The GSK definition is based on the definition provided by the ICH [[ICH, M3 \(R2\) 2009](#)].”

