6.2. Treatment Assignment

Study treatment in this protocol refers to the blinded investigational drug IV DNX, IV DNX placebo and the open label oral OSV. Subjects will be assigned to 15 mg FBE IV DNX, 50 mg FBE IV DNX or IV DNX Placebo, in accordance with the randomization schedule generated by Clinical Statistics, prior to the start of the study, using validated internal software.

A description of each regimen is provided in the table below:

Table 2 Treatment Regimens for Study 201023/DAHLIA

Treatment Arm	Sample Size per influenza season / study (3 influenza seasons)	Treatment Label	Treatment Regimen ^a
A	40/120	15 mg FBE DNX	15 mg FBE IV DNX given twice daily with 75 mg oral OSV given twice daily
B	40/120	50 mg FBE DNX	50 mg FBE IV DNX given twice daily with 75 mg oral OSV given twice daily
C	20/60	PBO	IV DNX placebo given twice daily with 75 mg oral OSV given twice daily

a. OSV dose adjustments may be made as indicated in the prescribing information.

Subjects will be randomized using the RAMOS NG system. This system will be used by the investigator or designee to register the subject.

Details of how to use the RAMOS NG system to register and randomize subjects is provided in the study reference manual (SRM).

Subjects meeting all eligibility criteria will be randomized 2:2:1 to one of three treatment groups in accordance with the central randomization schedule generated by Clinical Statistics prior to the start of the study, using validated internal software. Minimization criteria will be based on influenza medication prior to hospitalization (Relenza, Tamiflu, peramivir or other), number of days of symptoms prior to hospitalization (0-3, 4-6), subject origin prior to hospitalization (nursing home, rehabilitation unit, home).

All randomized subjects will take investigational drug or matching placebo twice daily for up to 5 days in the hospital.

Once a randomization number has been assigned, it must not be re-assigned.

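### The safety reviews for sentinel cohorts 2 and 3 rest on about 10 subjects over all arms with no balancing within the cohort, so the number given 50 mg DNX is left to chance

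*Protocol*

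**What the plan says.** Protocol 4.1.1 opens enrolment to renally impaired subjects in two steps. First, "approximately 10 subjects with mild renal impairment, defined as baseline creatinine clearance of 50-79 mL/min will be enrolled in sentinel cohort 2". After an acceptable IDMC outcome, "approximately 10 subjects with moderate renal impairment (defined as baseline creatinine clearance of 30-49 mL/min) will be enrolled in sentinel cohort 3". Between the steps, "Additional subjects with mild renal impairment will not be enrolled until the safety review is conducted by the IDMC". Each step is sized by total number enrolled; no minimum per arm, and no minimum on 50 mg, is given. Subjects with normal renal function go on enrolling alongside cohort 2, and mild-impairment enrolment resumes alongside cohort 3.

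On assignment, 6.2 says: "Subjects meeting all eligibility criteria will be randomized 2:2:1 to one of three treatment groups", from a central schedule. It adds: "Minimization criteria will be based on influenza medication prior to hospitalization", followed by symptom duration and where the subject lived before admission. Renal function and sentinel cohort are not listed, no block size is stated, and the way the schedule and the minimisation work together is not described.

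The reason for the steps is Captisol, which is cleared by the kidney. Section 4.1.1 gives 750 mg of it per 50 mg of DNX. The placebo is plain saline (footnote 1 to Table 1 in 6.1).

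**The concern.** The two renal reviews are there to show whether a Captisol-containing infusion is tolerated at each level of impairment. The load follows the dose: 750 mg per infusion at 50 mg, 750 × 15/50 = 225 mg at 15 mg, and none on placebo. The most informative subjects are those on 50 mg, and the placebo subjects are the only comparator without Captisol.

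Overall 2:2:1 balance does not carry down to a cohort of 10 that is drawn from a longer sequence and not used in balancing. If chance puts one or two of the 10 on 50 mg, a clean review says little about the highest load. It may nevertheless open the study to everyone at that renal level, two fifths of whom would be assigned 50 mg.

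**Working it through.** **The plan's own figures.** Table 2 in 6.2 gives 40/40/20 per season and 120/120/60 overall. Splitting 100 and 300 in the ratio 2:2:1 reproduces both exactly. The same ratio applied to 10 subjects gives an expected 4/4/2. The documents give no per-arm count for any sentinel cohort.

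**Inputs.** P(50 mg) = 2/5 = 0.4 and P(placebo) = 1/5 = 0.2 (6.2); n = 10 for cohorts 2 and 3 (4.1.1).

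**Independent assignment.** The number on 50 mg is Binomial(10, 0.4):

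- P(0) = 0.6^10 = 0.0060
- P(1) = 10 × 0.4 × 0.6^9 = 0.0403
- P(2) = 45 × 0.4² × 0.6^8 = 0.1209
- P(2 or fewer) = 0.167
- At least one of the two cohorts: 1 − (1 − 0.167)² = 0.307

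The number on placebo is Binomial(10, 0.2): P(0 or 1) = 0.8^10 + 10 × 0.2 × 0.8^9 = 0.107 + 0.268 = 0.376.

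If the approximate 10 is read as 8 to 12, P(2 or fewer on 50 mg) runs from 31.5% (n = 8) to 8.3% (n = 12).

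**Central list blocked, but not by cohort.** Block size is not stated, so I assumed permuted blocks of 5 or 10 and let the cohort's share of enrolment vary. Simulated P(2 or fewer on 50 mg), per cohort:

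| Cohort's share of enrolment | P(2 or fewer on 50 mg) |
|---|---|
| 20% | 14% |
| 33% | 12-13% |
| 50% | 9-10% |
| 75% | 4-7% |
| 100% | 0-5% |

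The low end of each range is for a cohort that starts at a block boundary. The last row does not match 4.1.1, where other subjects enrol at the same time. The working range is therefore about 4-14%.

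**What two subjects can show.** With no events in n subjects, the one-sided 95% upper bound on the event rate is 1 − 0.05^(1/n): 78% for n = 2 and 53% for n = 4. With a true rate of 20% (assumed), the chance of seeing at least one event is 1 − 0.8² = 36% with two subjects and 1 − 0.8⁴ = 59% with four.

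**Cohort 1.** Its entry rule is "Normal renal function: Baseline creatinine clearance within normal reference ranges (≥ 80 mL/min) for the first approximately 30 subjects enrolled". With n = 30, P(2 or fewer on 50 mg) is about 0.005%, so the point does not apply there.

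**The case against.** The strongest reply is that neither step opens on a headcount. The IDMC must report an acceptable outcome. It sees unblinded data (4.1), weighs all the evidence, compares treatment groups and can drop a dose (10.8.1). It would notice that only two subjects had received 50 mg, and an approximate cohort size leaves it room to ask for more. Its charter may even set a per-arm minimum. This stands as mitigation and limits the point to a cheap improvement. But the committee cannot create missing data, and nothing in the documents shows such a minimum.

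Second, the exposure concern can be overstated. Section 4.1.1 speaks of accumulation in severe impairment, and clearance below 30 mL/min is excluded. Section 4.6.1 predicts Captisol concentrations below those seen with a marketed product. The 15 mg arm also receives some, so about 8 of 10 subjects are exposed; P(4 or fewer exposed), from Binomial(10, 0.8), is 0.6%. Sentinel subjects also have twice-daily renal checks. All of this is fair. It softens the consequence but does not secure data at the highest load.

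Third, 16.7%, 31% and 38% are upper-end figures at n = 10, because they assume independent assignment. That is accepted, and the blocked range stands beside the first of them.

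A reader might also infer that the renal safeguards fail outright, because 4.6.1 adds an ad hoc nephrologist "if there are 10 subjects across all treatment arms withdrawn due to the renal stopping criteria", a number as large as a whole renal cohort. The documents do not support that. The count only adds a committee member, the same sentence allows one whenever renal expertise is needed, and the count is not limited to sentinel subjects. Numeric renal rules for individual subjects are in 5.4.4. The halting criteria are detailed in the unseen charter, and SAP 8.2.2 shows that creatinine rises feed into them.

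**Conclusion.** The point holds for cohorts 2 and 3 only. The plan leaves the number on 50 mg at each renal review to chance. Four is the expected number, but two or fewer has a probability of 16.7% per cohort under independent assignment (31% for at least one of the two), or about 4-14% per cohort under blocking that ignores the cohort. Having no more than one placebo subject has a probability of up to 38% at n = 10.

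The conclusion rests on three things: the balancing factors listed in 6.2 being complete, block sizes of 5 or 10 that are my assumption, and a cohort share of 20-75% of enrolment. It does not say that the IDMC would approve on thin data. The SAP reports that the study ended after 10 subjects were enrolled, so the point concerns the design as planned and any reuse of it.

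**What to change.** In 6.2, balance treatment assignment within each sentinel cohort in one of two ways:

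- Stratify the 2:2:1 schedule by sentinel cohort in blocks of 5. At 10 subjects this gives exactly 4/4/2. If a cohort closed at 8, two on 50 mg would still be possible, but only when both 50 mg slots of the second block are the last two: 1/C(5,2) = 10%, against 31.5% without stratification.
- Add sentinel cohort as a minimisation factor. This fits the existing method more easily but makes the 4/4/2 split likely rather than certain.

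If the IDMC charter already sets a minimum on 50 mg for each review, a sentence in 4.1.1 saying so would also answer the point.

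The cost is one more randomisation factor, which has to be reconciled with the existing minimisation, and the matching text in 6.2. No extra subjects, visits or procedures are needed. The gain is modest: four subjects without an event still leave an upper bound of 53%, and two placebo subjects remain a thin comparator.
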